Data will be collected through self-report, QST, and biological samples. The informed consent documents (hard copy), which include the participant's name and assigned identifier, will be stored in a locked cabinet in the PI's office located in the Kinesiology Department at the University of Wisconsin-Madison Natatorium building. These will be separate from the other study documents and only the PI will have access. All data will be coded using a personal identifier assigned to the participant after informed consent is signed, thus all collected data will be coded. All information collected on paper (i.e., age, HR, height, RPE, weight, questionnaire data, QST variables), besides the informed consent, will be stored in a locked cabinet in the Exercise Psychology Lab, which is part of the Kinesiology Department. Note: any personal health information collected will be self-report rather than through medical records and will be recorded on the demographic and pain history form. Thermal pain threshold will be recorded via Medoc software and files will be stored on a password protected secure server in the Exercise Psychology Lab. Similarly, accelerometer data will be stored on the same password protected secure server in the Exercise Psychology Lab. The accelerometer only collects information regarding physical activity behaviors (e.g., minutes per day spent in light-intensity activity, minutes per day spent in moderate-intensity physical activity, sedentary minutes per day). Data

downloaded from the device will be linked to each participants' unique study ID number. No information or data goes to the company (ActiGraph) that produces/sells the devices. After the devices are returned and downloaded, data will be deleted off of the accelerometer. Data will be imputed into a computer for data analysis where it will be stored in a secured file on the Exercise Psychology Lab server which is located in a password protected area with firewall protection and backed up daily. All team members will have access to the coded information located in the Exercise Psychology Laboratory. Biological samples (blood samples) will be stored in a freezer in the Biodynamics Laboratory located in the Natatorium at the University of Wisconsin-Madison after which they will be transferred to a container of dry ice and driven by the PI to [name] laboratory at the Medical College of Wisconsin. The blood samples then will be stored in [name] lab after which they will be exhausted. The blood samples will contain only the participant ID number, time of collection, and session date; thus, participants will not be able to be identified. Moreover, data for eligible participants will be kept and secured in a locked file cabinet in the Exercise Psychology Lab until the participant has either completed the study, removed themselves from participation, or is excluded from participation. If participants give consent to be contacted for future research, their contact information and screening data will be stored in a locked cabinet in the PI's office once the study is complete (see "Permission to Contact for Future Research List" section below for more information). All other screening data for eligible participants will be shredded upon participant completion, dropout, or exclusion of the study. Phone screening data from any interested potential participants not meeting inclusion criteria will be shredded immediately. Biological samples will be exhausted upon completion of endocannabinoid assay. Any link between coded data and directly identifiable data (i.e., names/phone number/email on the informed consent) will be shredded after 7 years. Coded data includes all data collected for the purposes of the study (i.e., questionnaire data, exercise data, accelerometer data, eCB results, and QST data) and will be kept indefinitely.

Permission to Contact for Future Research List

A permission to contact list will be generated from participants who provide consent to be contact for future studies. This list will consist of the contact information and screening data from only these individuals. The information will be stored in a locked cabinet in the PI's office. Only participants who are interested in the current study will be on the "permission to contact for future research" list and only the study team will have access to this list. Further, it will only be used to recruit for similar studies in the Exercise Psychology Laboratory. The list will be destroyed after 5 years. Generating this list will be helpful in recruiting breast cancer survivors with CIPN for future studies conducted by [name] Psychology Lab.

Sample/Specimen Collection

Blood samples will be collected by a trained phlebotomist using EDTA containing tubes (BD Vacutainer, K3E EDTA K3) and centrifuged. Plasma will be frozen at -80 C in a freezer in a designated area on the UW-Madison campus until all samples are collected. All samples will be driven by the PI to [name] lab at the Medical College of Wisconsin and will be stored in a freezer until analysis. No samples will include identifiable information and the results from the eCB assays will be shared between study team members using the participant ID numbers.

Study Procedures

[figure not shown]

Figure 1. Study flow chart.

References

1. American Cancer Society. Breast Cancer Facts & Figures 2017-2018. In. Atlanta: American Cancer Society, Inc.; 2017.

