hours prior to their study visit. Participants will attend one familiarization session, 45 minutes long, and two study visits, each 60-75 minutes long, to complete both the yoga and aerobic exercise sessions. There will be between 2 and 7 days between Study Visit #2 and Study Visit #3. All visits will be completed independently and participants will spend a total of 165-195 minutes completing this study. Session order (experimental vs. aerobic exercise) will be randomized and counter-balanced. See Figure 1 for a schematic of the study procedures.

The exercise stimuli will be matched on session duration (i.e., 40 minutes) and session intensity (using the ratings of perceived exertion scale, RPE).

Yoga Task: The yoga task will consist of 44 minutes of Iyengar yoga in a sound-dampened chamber. The yoga session will be pre-recorded and led by a certified yoga instructor who has previously worked with individuals with chronic medical conditions. The yoga task will consist of 7 minutes of light intensity poses (i.e., RPE 10-11) followed by 32 minutes of moderate intensity poses (RPE 12-14). The cool-down will consist of 5 minutes of light intensity poses (RPE 10-11). Participants will follow the pre-recorded video and will be instructed to participate to the best of her ability. Heart rate (HR) will be recorded continuously through a heart rate monitor and the session intensity and pain intensity will be recorded every five minutes. Session intensity will be monitored using the ratings of perceived exertion scale (RPE) (46). Pain intensity will be recorded using one item rated on a 0-10 scale from the painDETECT (42): “How would you assess your pain now, at this moment?” Participants will be encouraged to work at a moderate intensity for the 32 minute time period.

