Aerobic Exercise Task: The aerobic exercise task will consist of 44 minutes of aerobic exercise (i.e., walking) on a stationary treadmill. To match the yoga session, participants will undergo a 5-minute light intensity warm up (i.e., RPE 10-11) after which they will engage in 30 minutes of walking or jogging at a moderate intensity (i.e., RPE 12-14). Finally, participants will complete a 5 minute cool down at a light intensity (i.e., RPE 10-11). This procedure was based off previous research in our lab which demonstrated a significant increase in eCBs using this exercise stimulus. HR will be recorded continuously and RPE and pain intensity will be collected at 5-minute intervals. ***{Note: both exercise modalities have been employed in previous research in our lab without incident}***

Visit 1

During this session, participants will complete several questionnaires and be familiarized with the QST protocol. The questionnaires will include: informed consent, demographic and pain history questionnaire, the menstrual cycle log, the painDETECT, the Pain Catastrophizing Scale, and the Pain Diagram. Participants' questionnaires will be examined to determine the presence of chemotherapy-induced neuropathic pain as indicated by the painDETECT, Pain Diagram, and participant report of chemotherapy agent (found on the demographic and pain history form). If participants are found to be eligible, they will partake in the remaining procedures. If participants are found to be ineligible, they will be thanked for their participation and compensated \$15 for their time. The remaining familiarization procedures include recording their age, blood pressure, height, and weight. Further, patients will be familiarized with the pain testing and exercise protocols. In order to be familiarized with the pain testing, participants will undergo an

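### The two sessions are said to be matched at 40 minutes, but yoga is 44 minutes and the treadmill task is given as both 44 and 40

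*Combined protocol and SAP*

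**What the plan says.** All the relevant statements are in the protocol's Procedures section, before the description of Visit 1.

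- **Matching sentence:** "The exercise stimuli will be matched on session duration (i.e., 40 minutes) and session intensity". Intensity is to be matched on ratings of perceived exertion (RPE).
- **Yoga Task, total:** "The yoga task will consist of 44 minutes of Iyengar yoga in a sound-dampened chamber".
- **Yoga Task, phases:** "7 minutes of light intensity poses (i.e., RPE 10-11) followed by 32 minutes of moderate intensity poses", and then "The cool-down will consist of 5 minutes of light intensity poses". The length of the moderate phase is repeated: "Participants will be encouraged to work at a moderate intensity for the 32 minute time period".
- **Aerobic Exercise Task, total:** "The aerobic exercise task will consist of 44 minutes of aerobic exercise (i.e., walking) on a stationary treadmill".
- **Aerobic Exercise Task, phases:** "participants will undergo a 5-minute light intensity warm up (i.e., RPE 10-11) after which they will engage in 30 minutes of walking or jogging", at moderate intensity, and then "Finally, participants will complete a 5 minute cool down at a light intensity". The protocol introduces these phases as chosen to match the yoga session.

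The RPE targets are the same in both tasks (10-11 for light phases, 12-14 for moderate), so only duration is in conflict.

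**The concern.** The study compares yoga with aerobic exercise within the same participants, and the Data Analysis section tests this with condition by time repeated measures ANOVAs. Duration and RPE are the only two properties on which the sessions are claimed to be matched. As written, the duration claim cannot be true together with the task descriptions, and staff do not have one treadmill instruction they can carry out.

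The yoga session is a pre-recorded video, so its length is fixed. If the treadmill phases are run as listed, the difference in duration is the same in every participant. Randomising and counterbalancing session order does not remove it, because it belongs to the condition and not to the order. The post-exercise blood draw follows immediately on task completion, so in the yoga condition it would also come after a longer task.

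**Working it through.** **Inputs** (minutes, from the Yoga Task and Aerobic Exercise Task paragraphs)

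| | Yoga | Treadmill | Yoga minus treadmill |
|---|---|---|---|
| Light warm-up | 7 | 5 | +2 |
| Moderate phase | 32 | 30 | +2 |
| Light cool-down | 5 | 5 | 0 |
| **Sum of phases** | **44** | **40** | **+4** |
| Total stated for the task | 44 | 44 | 0 |
| Matched duration claimed | 40 | 40 | 0 |

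**Step 1: do the stated totals reproduce?** Yoga: 7 + 32 + 5 = 44, which agrees with its stated total but not with the claimed 40. Treadmill: 5 + 30 + 5 = 40, which agrees with the claimed 40 but not with its stated total of 44.

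**Step 2: could the 40 minutes leave out warm-up or cool-down?** For yoga, 7 + 32 = 39, 32 + 5 = 37, and the moderate phase alone is 32. No combination of yoga phases gives 40, so this does not rescue the matching sentence.

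**Step 3: reading A, staff follow the listed phases.** Yoga is longer by 44 − 40 = 4 minutes, or 4/40 = 10% of the treadmill session. Of these, 7 − 5 = 2 are warm-up and 32 − 30 = 2 are moderate exercise; the cool-downs are equal. The sessions are not matched on duration.

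**Step 4: reading B, the 44-minute treadmill total governs.** The totals match, but 44 − 40 = 4 treadmill minutes have no phase or RPE target; 4/44 = 9.1%. The documents do not say how these minutes are used. Assume each is either light or moderate, and let k of the 4 be moderate:

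- treadmill moderate time = 30 + k, which runs from 30 to 34 minutes for k = 0 to 4;
- yoga minus treadmill moderate time = 32 − (30 + k) = 2 − k, which runs from +2 to −2;
- moderate time matches only when k = 2.

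**Step 5: worst case over both readings.** The difference is at most 4 minutes in total and at most 2 minutes at moderate intensity, in either direction.

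**The case against.** The strongest case on the other side is that this is a leftover from editing and of little consequence. Both task paragraphs open with 44 minutes, the yoga phases sum to 44, and the treadmill phases are meant to match yoga. An incomplete change from 40 to 44 would explain all of it. The study is an exploratory pilot, intensity is set by RPE bands and not to the minute, and the protocol treats 30-50 minutes of exercise as one effective range for endocannabinoids. Totals of 40 and 44 minutes, and moderate phases of 30 to 34, all lie inside that range. The ANOVA does not use session duration, and the pre-post effect sizes within each session do not depend on matching.

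These points stand as limits on importance. They do not remove the contradiction: the editing explanation is inference, and no other text reconciles the figures. Figure 1 is not available to check, but a figure could not make these sentences agree.

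A second objection concerns the remedy. The protocol says the treadmill procedure rests on the laboratory's previous research, in which this stimulus raised endocannabinoids. Lengthening the phases might depart from that precedent if it was 5/30/5; the documents do not say. This is a fair reason to allow the alternative of dropping the duration claim. It does not rule out 44 minutes, which is the total the protocol itself states for the treadmill.

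**Conclusion.** The inconsistency is real and the text is wrong as written. If the phases are followed, yoga exceeds the treadmill session by 4 minutes (2 warm-up, 2 moderate), the same for everyone. If the 44-minute total is followed, 4 treadmill minutes are unassigned, and the difference in moderate time could be anywhere from +2 to −2 minutes, assuming each unassigned minute is either light or moderate.

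The size and direction of any effect on pain, mood or endocannabinoid outcomes cannot be derived from the documents, and there is no basis for expecting a large one. The correction should be made because duration matching is a stated design property behind the main comparison, and because staff need a single dose instruction.

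**What to change.** Since the yoga video is already fixed at 44 minutes, set the treadmill phases to 7 minutes light, 32 minutes moderate and 5 minutes cool-down, and change 40 to 44 in the matching sentence. If the investigators prefer to keep the 5/30/5 treadmill procedure from their previous work, correct its stated total to 40 and remove the claim that the sessions are matched on duration.

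In either case, report the minutes delivered in each phase alongside the RPE and heart rate summaries already planned. Heart rate is recorded continuously, so elapsed time is available; staff would need only to note when each phase begins and ends.

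The cost is a text correction in Procedures and, under the first option, a treadmill script aligned with the video. No participants, visits or measurements are added, and the analysis does not change.

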Based on a previously published clinical study suggesting large reductions in pain following yoga (39), a statistical power analysis was performed for sample size estimation based on a large effect size. Using Cohen's f effect size (ES) of .4, alpha = .05, and power = .80, the total sample size needed for this study is N = 10 (GPower 3.1). We will recruit up to 30 individuals to account for participant attrition and for those who may be excluded at the familiarization session.

Reasons for exclusion include inability to complete exercise sessions, neuropathic pain which developed from something other than chemotherapy treatment, or if a participant reports she did not receive a chemotherapy agent that is known to cause neuropathy.

Inclusion Criteria

Inclusion criteria will be as follows:

- A diagnosis of breast cancer (stage 0-III),
- no evidence of active disease (i.e., recurrence, bone metastases, etc),
- presence of painful polyneuropathy, with onset coinciding or developing after receiving chemotherapy agents that in the opinion of the research team is likely to have caused such symptoms,
- at least six months since last active cancer treatment, with no further planned treatment (Note. active treatment is defined as surgery, chemotherapy, or radiation),
- the participant agrees to use the safety stop feature on the treadmill if needed,
- at least 18 years of age,
- and their physicians has provided consent for them to participate in yoga and aerobic exercise sessions.

Note. The inclusion criteria “the participant agrees to use the safety stop feature on the treadmill if needed” and “and their physicians has provided consent for them to participate in yoga and aerobic exercise sessions” were added at the request of the UW Carbone Cancer Center PRMC. Their correspondence is included in the supplementary section of the IRB application.

Exclusion Criteria

Exclusion criteria will include:

- undergoing current chemotherapy or radiation treatment for cancer,
- taking anticoagulant therapy,

- uncontrolled medical conditions (i.e., uncontrolled hypertension, heart disease, stage 4 liver disease, end-stage renal disease, end-stage pulmonary disease, etc),
- stroke or myocardial infarction in the past 6 months,
- being pregnant or planning to become pregnant,
- severe mobility constraints (e.g., confined to a wheelchair),
- having a history of light headedness or fainting during blood draws or physical activity,

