The design of this study is an exploratory within subject, repeated measure design where participants complete pre-post measures during two study visits (i.e., aerobic and yoga tasks). Descriptive statistics will be reported on the demographic variables (i.e., age, ethnicity, height, etc.) and CIPN (i.e., painDETECT and pain diagram questionnaires) to characterize the sample. RPE and HR data will be summarized to describe the exercise stimuli. We will conduct condition (aerobic, yoga) x time (pre-, post-) repeated measures ANOVAs to determine the influence of yoga and aerobic exercise on pain (QST outcomes, SF-MPQ, and VASs), psychological outcomes (POMS, STAI), and eCBs (2-AG, AEA). Further, effect sizes for pre-post changes in dependent variables will be calculated using Cohen's d to understand the strength of the effect. Significant interaction effects will be examined using simple effects and Holm's procedure will be applied. Data which violate the assumption of normality will be logarithmically transformed.

Study Coordination

This study will involve collaboration between the University of Wisconsin-Madison and the Medical College of Wisconsin. The University of Wisconsin-Madison will serve as the lead site for this study, thus [name], PI, will oversee all study activities. In addition, she will be responsible for coordinating between UW-Madison and the Medical College of Wisconsin.

Procedures involving recruitment will be conducted at the University of Wisconsin-Madison and will be supervised by [name]. Data collection and data analysis will be conducted at UW-Madison under the supervision of [name]. Analysis of the blood samples will be conducted at the Medical College of Wisconsin under the supervision of [name]. These samples will be shipped to [name] who will supervise the eCB assays. [name] and [name] will communicate using email throughout the duration of eCB assay process. [name] has visited [name] lab several times and they have previously collaborated in eight prior studies.

Data Collection

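### A participant who completes Visit 2 but not Visit 3 drops out of every planned ANOVA, and the pre-post change is overstated if poor responders are the ones who do not return

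*Combined protocol and SAP*

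**What the plan says.** The Data Analysis section describes a "repeated measure design where participants complete pre-post measures during two study visits", one visit for yoga and one for aerobic exercise. The inferential method is: "We will conduct condition (aerobic, yoga) x time (pre-, post-) repeated measures ANOVAs to determine the influence of yoga and aerobic exercise on pain". The same sentence extends it to the psychological and endocannabinoid outcomes. Cohen's d for pre-post change is added, without saying who enters it.

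Under Procedures, session order "will be randomized and counter-balanced", and the sessions are on different days: "There will be between 2 and 7 days between Study Visit #2 and Study Visit #3".

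The Sample Size Justification uses "effect size (ES) of .4, alpha = .05, and power = .80" to reach N = 10, and then says: "We will recruit up to 30 individuals to account for participant attrition and for those who may be excluded at the familiarization session".

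No section names an analysis population, a missing-data rule, a model that accepts incomplete participants, or a sensitivity analysis. The word imputed in Data Collection refers to entering data into a computer. That section also says coded study data are kept indefinitely, so the record of a completed Visit 2 would still be on file.

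**The concern.** By the end of Visit 2 a participant has given two blood samples, two rounds of sensory testing and two questionnaire packets, all under a randomised order. If she does not come back, she has two of the four cells that the ANOVA needs, and her session is lost for every outcome.

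Whether she returns is settled after she has experienced the first session. If those who felt worse are less likely to return, the people left in the ANOVA are on average better responders, and the time effect looks larger than it is. That matters for Aim 1, which asks what each modality does to pain and psychological responses, and for the stated use of the results in designing later interventions. Recruiting more people restores the count but does not change who is missing.

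**Working it through.** **1. The plan's own figure.** For a within-subject F test, λ = f²·N·m/(1 − ρ). With f = 0.4 and N = 10 from the plan, and m = 4 measurements, ρ = 0.5 and no sphericity correction assumed, λ = 0.16 × 10 × 4/0.5 = 12.8 on 3 and 27 df. Power is 0.806, so N = 10 is reproduced. With 9, 8 or 7 complete participants the same formula gives 0.751, 0.684 or 0.604. Ten complete pairs need 10/0.9 → 12, 10/0.8 → 13 or 10/0.7 → 15 starters at 10, 20 or 30% loss. The ceiling of 30 can cover the loss in numbers.

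**2. Inputs for the bias (all assumed).** Each session's improvement has mean 0.80 and SD 1. The 0.80 is 2f. The correlation r between a person's two session changes is .3 to .6, the order split is 1:1, and 2 of 12 or 5 of 15 do not return.

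**3. Complete-case bias.** Suppose selection shifts the returners' mean first-session change by k. Their second-session change shifts by r·k. Each condition is half first sessions and half second sessions, so its complete-case mean shifts by (1 + r)k/2.

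If the worst first-session responders are lost, k is the sum of the expected extreme normal order statistics divided by the number returning:
- 2 of 12: (1.629 + 1.116)/10 = 0.274. The shift is 0.65 × 0.274 = 0.178 (r = .3) to 0.80 × 0.274 = 0.220 (r = .6), which is 22 to 27% of 0.80.
- 5 of 15: (1.736 + 1.248 + 0.948 + 0.715 + 0.516)/10 = 0.516. The shift is 0.336 to 0.413, which is 42 to 52%.

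Simulation agrees with these figures. It also covers moderate selection, in which the log-weight for loss rises by 1 per SD of worse first-session change:

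| Lost | Moderate selection | Worst responders lost |
|---|---|---|
| 2 of 12 | 13–15% too large | 22–27% too large |
| 5 of 15 | 27–31% too large | 43–52% too large |

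**4. When the bias is absent or reversed.** Under random loss k = 0, so there is no bias. The standard error of the pre-post change is about 5 to 15% larger than with all sessions used. If the best responders leave, the sign flips. At 20% loss and r = .5, in large samples, k = 0.280/0.80 = 0.35 and the estimate is 0.80 − 0.75 × 0.35 = 0.54.

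**5. The yoga-minus-aerobic contrast.** With equal true changes both conditions shift by the same (1 + r)k/2, so a true difference of 0 stays 0. With true changes of 0.80 and 0.30, 10 to 30% loss and r from .2 to .8, a true difference of 0.50 becomes 0.48 to 0.50 under gradual selection and 0.44 to 0.49 if the worst responders leave.

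**6. Which model repairs it.** A REML fit to all sessions that carries the between-session correlation of change gives 0.80 to 0.82 in the step 3 scenarios. That correlation comes from a participant x time random effect. Random effects for participant and visit within participant cancel out of a pre-post difference. A model with only those two treats the session changes as independent and averages the changes available. Its shift is (returners)/(all sessions) × r·k. For 5 of 15 and r = .6 this is 10/25 × 0.6 × 0.516 = 0.124, about 15% of 0.80.

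That smaller model also fails to match the planned ANOVA when nothing is missing. In one complete simulated data set the ANOVA gave F = 0.363 for time and 5.154 for the interaction. The two-term model gave 0.67 and 1.49. Adding participant x time reproduced 0.363 and 5.154.

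**The case against.** The strongest reply is that the harm is conditional. The documents give no between-visit dropout rate and no evidence that poor responders leave. The gap is at most 7 days, and the gift card is paid only after all three visits, which encourages return. The study is described as exploratory and as a comparison of yoga with aerobic exercise, and step 5 shows that this comparison is almost untouched. All of this stands and limits the point to the pre-post change.

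A reader might infer more than the documents support:
- **That the plan states listwise deletion.** It does not. Deletion follows from the named method as usually run.
- **That two thirds are expected to drop out, from 30 recruited for 10 needed.** The 30 is a ceiling that also covers exclusions at familiarization, before any exercise session. It is not a dropout rate.
- **That Cohen's d is necessarily affected.** Its analysis set is not stated, and it could be computed for each condition from every completed session.
- **That only people who did well would remain.** Selection would shift the average; it would not remove every poor responder.

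The reply does not supply a rule for someone with Visit 2 only, and a larger intake cannot correct selective loss.

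**Conclusion.** The point holds for the time effect. The planned ANOVA has no place for a participant with Visit 2 only. If non-return is related to a poor first session, the pre-post change is overstated by about 13 to 27% with 2 of 12 lost and about 27 to 52% with 5 of 15 lost. These sizes rest on an assumed change of 0.80 SD, correlations of .3 to .6, and the loss counts and selection patterns in the working; none of these comes from the documents. The cost under random loss is precision only, and the direction reverses if good responders leave. It would be wrong to conclude that the modality comparison is materially biased. For an exploratory pilot this is a change that should be made because it is cheap, not a flaw that invalidates the design.

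**What to change.** In Data Analysis, replace the repeated-measures ANOVA with a linear mixed model:
- Fixed effects: condition, time and condition x time.
- Random effects: participant, visit within participant, and participant x time.
- Estimation: REML with Kenward-Roger degrees of freedom.
- Analysis set: every randomised participant with at least one completed session.

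Take the pre-post change and its effect size from this model, which also settles who enters Cohen's d. Keep the complete-case ANOVA as a sensitivity analysis, and report non-returners by sequence.

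The participant x time term must not be omitted. With it, and with no missing data, the tests equal those of the planned ANOVA as long as no variance estimate is at zero.

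The cost is one paragraph and slightly more analysis work, with no added participants, visits or measures. The model assumes that non-return depends only on observed data such as the Visit 2 results. With about 10 participants it may meet zero-variance or convergence problems, so the text should say what will be done then.
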